2.2 Randomization

Randomization will occur cluster-wise on level of the practices where the enrolled GPs work. A statistician external to the study group will carry out stratified randomization into the active or control intervention group using the Shiny Balancer tool, which facilitates balanced allocation in cluster-randomised trials (1).

Stratification will occur according to the following factors:

- Participation status in the cantonal HPVv program at inclusion (yes/no).
- Estimated number of HPVv administered during the baseline period (4 categories, see section 3.3.1).

GPs enrolling in the trial when randomization of their practice has already taken place will be allocated to the corresponding study arm. GPs will need to be registered in the cantonal HPVv program before initiation of outcome measurements.

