4.2.3 Analysis of the Primary Objective

To analyze the primary objective, we will model the count of first administered HPVv doses at T6 using mixed-effect Poisson regression. The outcome variable will be the count of first HPVv doses administered by each GP at each of the time points T3 or T6. GP-level random intercepts will account for intra-GP correlation. The following fixed effects will define the grouping variables of the data set:

- Study arm (binary with levels control; active)
- Time point (binary with levels T3; T6)
- Baseline HPVv count (categorical with levels Never; Rarely (1–5 doses); Occasionally (6–10 doses); Regularly (at least 11 doses))
- GP gender (binary with levels male; female)
- GP age in years (continuous)
- GP workload (categorical with levels < 60%; 60–79%; 80–100%; based on the distribution of consultation counts according to workload in Swiss primary care (4))
- GP participation status in the cantonal HPVv program at inclusion (binary with levels yes; no)
- Patient gender (binary with levels male; female).

Each fixed effect other than the study arm will be included in the final model if a corresponding univariate analysis results in a *p*-value ≤ 0.2 .

The Poisson regression model will be assessed for overdispersion based on an asymptotic chi-squared test for the sum of squared residuals (5, 6). If the null hypothesis of no overdispersion is rejected at the 0.05 level, we will replace the Poisson model by a negative binomial model with the same fixed- and random-effect structure. A quasi-Poisson model will be considered as an alternative in case of an observed linear variance-to-mean relationship (7).

Rejection of the null hypothesis related to the primary objective (the effect associated with the study arm is equal to zero) will be based on the parameter estimate of study arm and its 95% confidence interval in the final model.

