4.2.4 Analysis of the Secondary Objectives

For the secondary objectives, we will use the following procedures:

- (1) Analogous models as for the primary objective, using the first HPVv dose count at the respective time point and assessing the coefficient estimate of the study arm together with 95% confidence intervals.
- (2) Analogous models as for the primary objective, but using the count of all administered HPVv doses instead of the number of first HPVv doses at the respective time points as the outcome variable. We will base assessment of this objective on the estimated coefficient of the study arm for the respective time points together with 95% confidence intervals.
- (3) We will model this objective with logistic regression. The binary outcome variable will indicate whether the overall count of administered HPVv doses at T6 will have increased with respect to the value indicated for Pb. Model covariates will include GP gender, workload (categorized as for the primary objective), and participation status in the cantonal HPVv program at inclusion.
- (4) To assess this objective, we will use logistic regression on a binary outcome indicating, for each GP, whether their HPV knowledge score will have increased from Ti to T6. The model will include the following covariates: study arm, baseline HPV knowledge score, GP gender, GP workload (categorized as for the primary objective), and participation status in the cantonal HPVv program at inclusion.
- (5) We will assess this objective by a logistic regression model analogous to the model for secondary objective 4. The binary outcome variable will indicate, for each GP, whether their HPVv attitude score will have increased from Ti to T6. Adjustment will occur for the baseline HPVv attitude score instead of the HPV knowledge score.
- (6) Tabulation and assessment of group differences as described in section 4.2.1.
- (7) Tabulation and assessment of group differences as described in section 4.2.1.

For each of the fitted regression models, we will report the results and inferred implications of standard model diagnostics procedures, such as assessment for overdispersion, residual and random effect analyses, influential point analyses, and checks for multicollinearity. Accordingly, we will adapt models as necessary (e.g., by log-transforming continuous variables, by excluding ill-defined variables from the model equations or by considering non-parametric alternatives where deemed appropriate).

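### A univariate p ≤ 0.2 screen decides whether the two stratification factors, and even time point, enter the primary model; they should always be included

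*SAP*

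**What the plan says.** **Randomisation (SAP 2.2).** Practices are allocated as follows: "A statistician external to the study group will carry out stratified randomization into the active or control intervention group using the Shiny Balancer tool". Two stratification factors are listed:
- "Participation status in the cantonal HPVv program at inclusion (yes/no"
- "Estimated number of HPVv administered during the baseline period (4 categories, see section 3.3.1"

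**Primary model (SAP 4.2.3).** First-dose counts per GP at T3 and T6 go into a mixed-effects Poisson model with GP random intercepts. The candidate fixed effects are study arm, time point, baseline HPVv category, GP gender, GP age, workload, programme status and patient gender. The rule is then: "Each fixed effect other than the study arm will be included in the final model if a corresponding univariate analysis" meets the threshold, namely "corresponding univariate analysis results in a *p*-value ≤ 0.2". The primary null hypothesis is judged on the arm estimate and its 95% confidence interval in the model that remains.

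**Secondary models (SAP 4.2.4).** Objectives 3 to 5 have fixed covariate lists that include workload and programme status, with no screen. The section closes with a paragraph on diagnostics for every fitted regression model, which says: "Accordingly, we will adapt models as necessary".

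**The concern.** Both stratification factors are on the screened list, so the outcome data decide whether the primary analysis adjusts for the factors by which the trial randomised. If a prognostic stratification factor is left out, the model-based standard error does not credit the balance that stratification achieved. The interval is then somewhat too wide and the test conservative.

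The screen also covers time point, which distinguishes the T3 and T6 rows, and patient gender, which does the same if counts are split by it. These terms belong to the layout of the data and should not depend on a p-value.

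Finally, the covariate set of the confirmatory model is known only once outcomes have been analysed, whereas secondary objectives 3 to 5 are fully listed in advance.

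**Working it through.** **1. Is anything exempt or restored?** In 4.2.3 only study arm is exempt. Section 4.2.5 repeats the analysis in the per-protocol population and with practice-level random intercepts, 4.2.6 repeats it within baseline categories, and 4.3 adds multiple imputation. None refits the primary model with both stratification factors forced in.

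**2. How often would a stratification factor be dropped?** The SAP gives no effect sizes for these factors, so the following are assumptions: 20% of GPs outside the programme, true rate ratio 0.6, mean 5 doses per GP, between-GP variance 0.7 on the log scale. Section 2.4 states 33 GPs without saying whether that is the total or per arm, so both 33 and 66 in total are shown.

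- Variance of one GP's log count ≈ 1/5 + 0.7 = 0.90.
- 66 GPs (13 outside, 53 inside): SE = √(0.90 × (1/13 + 1/53)) = 0.294; z = ln(0.6)/0.294 = −1.74.
- 33 GPs (7 and 26): SE = √(0.90 × (1/7 + 1/26)) = 0.404; z = −1.26.
- p > 0.2 means |Z| < 1.2816.

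| True rate ratio | Dropped, 66 GPs | Dropped, 33 GPs |
|---|---|---|
| 0.6 | 32% | 50% |
| 0.7 | 52% | 64% |

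A factor unrelated to the outcome is dropped 80% of the time by construction.

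**3. What does dropping that factor cost?** Its log-scale variance is 0.2 × 0.8 × (ln 0.6)² = 0.042, which is 6% of 0.7. The ratio of interval widths is √(0.90/(0.90 − 0.042)) = 1.024, so about 2% wider. At a rate ratio of 0.7 it is about 1%.

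**4. Simulation of the rule.** There were 4,000 trials per scenario, with GPs allocated 1:1 within strata, 70% in the programme, mean count 3 and GP standard deviation 0.6 on the log scale. One row per GP was analysed by a linear model on log(count + 0.5) as a stand-in for the mixed count model. All of these settings are assumptions. Factor effects ran from none to strong (log rate ratio 0.4 for programme status and 0.4 per baseline category). Power is for an arm log rate ratio of 0.45.

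| Quantity | Screened | Both forced in | Both omitted, strong effects |
|---|---|---|---|
| At least one factor dropped, 33 GPs (no arm effect) | 69–96% | 0 | – |
| At least one factor dropped, 66 GPs (no arm effect) | 44–96% | 0 | – |
| Type I error | 0.046–0.056 | 0.044–0.057 | 0.031–0.033 |
| Power, strong effects, 33 GPs | 0.294 | 0.300 | 0.230 |
| Power, strong effects, 66 GPs | 0.572 | 0.575 | 0.488 |

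Across all scenarios, power under the screen was within about 0.02 of forced inclusion.

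**The case against.** The screen is a mechanical rule written down in advance, and section 4.4 has the statistician receive exports blinded for study arm. That limits selection driven by the treatment contrast. Strong factors tend to survive a p ≤ 0.2 screen and weak ones cost little when lost, which is why the simulation shows almost no damage. This stands, and it sets the size of the point. It does not fix the model before outcomes are seen, and it does not explain why the factors used for randomisation should be optional.

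Four stronger readings are tempting but not supported:

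- **A much wider interval.** If the dropped factors explained half of the between-GP variance, the interval would be √(0.90/0.55) = 1.28 times as wide. A single 3-degree-of-freedom factor of that strength would rarely be dropped. With noncentrality 33 × 0.35/0.55 = 21 it fails the screen in about 0.3% of trials with 33 GPs. With the larger denominator 0.90 (noncentrality 12.8) it fails in about 4%. With 66 GPs the figure is below 0.1% either way. The 28% should not be set beside the 32–50% drop rates, which belong to a weak factor.
- **An invalid test.** Type I error stayed near nominal under the screen, and omission errs on the conservative side.
- **A changing estimand.** With a log link and normal random intercepts, dropping a balanced baseline covariate alters precision and barely moves the rate ratio.
- **Free adaptation of the primary model.** The adaptation paragraph stands under the secondary objectives. It can be read as covering the primary model, but the SAP does not say so outright.

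**Conclusion.** The point holds as one of pre-specification and consistency with the randomisation. As written, the primary model can lose either or both stratification factors and the time-point term on the strength of a univariate p-value, with no analysis that puts them back. Under the stated assumptions, dropping programme status is a common event (about one trial in three with 66 GPs, one in two with 33).

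The expected statistical loss is small: about 2% in interval width for that factor, and little change in type I error or power. Larger losses, such as power falling from 0.575 to 0.488 with 66 GPs, arise only if two strong stratification factors are both omitted, which the screen makes unlikely. A reader might infer that the primary analysis will ignore the design or that its result would be invalid; the text and the calculations support only that it may fail to reflect the stratification.

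The figures rest on assumed effect sizes, variances and GP numbers, and on a simplified analysis model. The reading of the SAP text does not depend on them. The change is worth making because it is almost free.

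**What to change.** In section 4.2.3, delete the p ≤ 0.2 rule for the primary model and fix the model in advance:

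- Always include study arm, time point, baseline HPVv category and programme status.
- Include workload as a pre-specified prognostic covariate.
- Keep patient gender as a fixed term if the rows are split by it; otherwise aggregate counts over it.
- Put GP age and GP gender in a sensitivity model.
- State that the data-driven adaptation in the last paragraph of 4.2.4 applies, for the primary objective, only to sensitivity analyses.

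Secondary objectives 1 and 2 use models analogous to the primary one and would inherit the fixed list. The cost is a few sentences of SAP text and a few degrees of freedom for covariates that may prove weak.

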4.2.4 Analysis of the Secondary Objectives

For the secondary objectives, we will use the following procedures:

- (1) Analogous models as for the primary objective, using the first HPVv dose count at the respective time point and assessing the coefficient estimate of the study arm together with 95% confidence intervals.
- (2) Analogous models as for the primary objective, but using the count of all administered HPVv doses instead of the number of first HPVv doses at the respective time points as the outcome variable. We will base assessment of this objective on the estimated coefficient of the study arm for the respective time points together with 95% confidence intervals.
- (3) We will model this objective with logistic regression. The binary outcome variable will indicate whether the overall count of administered HPVv doses at T6 will have increased with respect to the value indicated for Pb. Model covariates will include GP gender, workload (categorized as for the primary objective), and participation status in the cantonal HPVv program at inclusion.
- (4) To assess this objective, we will use logistic regression on a binary outcome indicating, for each GP, whether their HPV knowledge score will have increased from Ti to T6. The model will include the following covariates: study arm, baseline HPV knowledge score, GP gender, GP workload (categorized as for the primary objective), and participation status in the cantonal HPVv program at inclusion.
- (5) We will assess this objective by a logistic regression model analogous to the model for secondary objective 4. The binary outcome variable will indicate, for each GP, whether their HPVv attitude score will have increased from Ti to T6. Adjustment will occur for the baseline HPVv attitude score instead of the HPV knowledge score.
- (6) Tabulation and assessment of group differences as described in section 4.2.1.
- (7) Tabulation and assessment of group differences as described in section 4.2.1.

For each of the fitted regression models, we will report the results and inferred implications of standard model diagnostics procedures, such as assessment for overdispersion, residual and random effect analyses, influential point analyses, and checks for multicollinearity. Accordingly, we will adapt models as necessary (e.g., by log-transforming continuous variables, by excluding ill-defined variables from the model equations or by considering non-parametric alternatives where deemed appropriate).

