2.8 Timing of Study Assessments

For each GP included into the study, we define the following timings:

- Baseline period Pb: A consecutive period of three months as recent as possible, but entirely before the intervention date Ti. Study participants will be asked to provide estimates of the number of HPVv doses administered during this period, which will be used for stratified randomization (see sections 2.2 and 3.3.1).
- Intervention date Ti: The day of delivery of the active and control intervention in the active intervention arm or of the control intervention in the control intervention arm. A questionnaire assessing knowledge on HPV and attitudes concerning HPVv will be administered at Ti, right before delivery of the intervention.
- Study start T0: The day of start of vaccination counting, usually scheduled on the 1st of the respective month following Ti. If Ti falls within the first week of a month, T0 is usually scheduled on the 15th of the same month.
- Follow-up at T3, T6, and T12: The dates at three, six and twelve months, respectively, after the study start T0. The questionnaire on HPV knowledge and HPVv attitudes will be delivered a second and final time at T6.
- **Study period**: The time interval between T0 and T6, which is the time interval relevant to the primary objective of the study.
- Follow-up period: The time interval between T6 and T12.
- Study end: The follow-up date T12, which indicates the end of all vaccination documentation.

3 Statistical Principles

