3.3.1 Baseline Data

GPs will be asked to provide the total number of vaccination doses administered during Pb for each of the vaccinations that will also be reported during the study and follow-up periods. GPs will be provided the choice among Never; Rarely (1–5 doses); Occasionally (6–10 doses); Regularly (at least 11 doses). For Pb, no information will be collected on demographic data of patients who obtained the vaccination or on whether the vaccinations were administered as first/second/third doses or booster vaccinations.

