4.1.2 Secondary Objectives

- (1) To compare the first-dose HPVv counts at T3 and T12 between the intervention group and the control group.
- (2) To compare the number of overall HPVv counts at T3, T6, and T12 between the intervention group and the control group.
- (3) To compare the change of overall HPVv counts at T3, T6 and T12 with respect to Pb between the intervention group and the control group.
- (4) To compare the change in HPV-related knowledge at T6 with respect to Ti (before delivery of the intervention) between the active intervention group and the control group.
- (5) To compare the change in attitudes towards HPVv at T6 with respect to Ti (before delivery of the intervention) between the active intervention group and the control group.
- (6) To describe demographic characteristics of patients obtaining HPVv (gender and age).
- (7) To describe the following characteristics of administered HPVv: first dose or later vaccination, request of patient or recommendation by GP (or both), and HPVv administered alone or in combination with other vaccines.

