4.5 Statistical Software

Statistical analysis will be performed with the software R version 4.1.0 or higher (R Foundation for Statistical Computing, Vienna, Austria) (8).

5 Safety Analyses

This study will include no safety analyses, since no safety data collection will be required (2).

6 Reporting Conventions

For summary statistics, we will use one decimal place more than for the data from which they originate. We will make exceptions were deemed appropriate, such as for reporting of extremal values, where we will use the same number of decimal places as for the data from which they originate.

We will report quantities derived from regression models (coefficient estimates with confidence intervals and variance estimates) and values of test statistics up to three decimal places. We will report p-values of at least 0.001 up to three decimal places, and p-values smaller than 0.001 as "< 0.001".

7 Summary of Changes to the Protocol

The following points needed changes with respect to indications in the study protocol:

- Included GPs will not be asked for a precise number of administered vaccinations during Pb, but will provide a categorical estimate.
- Accordingly, the primary and secondary outcomes will not compare changes from T0 to the respective time points, but will assess the absolute HPVv uptake between T0 and the respective time points.
- Duration of Pb will be reduced from 6 months to 3 months due to practicability reasons.
- Accordingly, to ensure comparability with HPVv numbers during the baseline period, the measurements at 2 and 4 months after T0 will be replaced by one single measurement at 3 months after T0.

References

1. Grischott T. The Shiny Balancer – software and imbalance criteria for optimally balanced treatment allocation in small RCTs and cRCTs. BMC Med Res Methodol 2018; 18(1):108.

2. [name]. Impact of a multifaceted, targeted intervention on the HPV vaccination rate in Swiss Primary Care: A cluster randomized controlled study (Study protocol version 1.0). 2021.

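### The model for secondary objective 3 lists no study arm, covers T6 only, and judges increase by setting a six-month count against a three-month baseline category

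*SAP*

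**What the plan says.** SAP Section 4.1.2 states secondary objective 3 as: "To compare the change of overall HPVv counts at T3, T6 and T12 with respect to Pb between the intervention group and the control group".

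Section 4.2.4, item (3), plans one logistic regression for it. The outcome is binary: "whether the overall count of administered HPVv doses at T6 will have increased with respect to the value indicated for Pb". The covariates are then listed: "Model covariates will include GP gender, workload (categorized as for the primary objective), and participation status in the cantonal HPVv program at inclusion". Item (4), the next model, is written differently: "The model will include the following covariates: study arm, baseline HPV knowledge score, GP gender", followed by further covariates.

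Section 2.8 defines Pb as "A consecutive period of three months as recent as possible, but entirely before the intervention date Ti". Under Section 3.3.1 the Pb value is not a number. It is one of four answers: none, 1 to 5, 6 to 10, or at least 11 doses. Section 7 explains that, because of this, the outcomes "will assess the absolute HPVv uptake between T0 and the respective time points". It also says that the three-month measurement was introduced so that counts could be compared with the baseline period.

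**The concern.** Four things in item (3) do not fit the objective.

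- The objective is a contrast between arms, but the listed model has no arm term.
- The objective names three time points, but only T6 is modelled. The omitted T3 is the one whose window has the same length as Pb.
- The T6 count covers T0 to T6, twice the length of Pb, and no offset or scaling is given. A GP whose rate has not changed is expected to give twice as many doses.
- The baseline is a category with an open top level, and no rule says when an exact count has increased over a category.

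Item (3) is the only planned analysis of change from baseline in vaccination counts. If it is run as written, objective 3 goes unanswered, and the reported share of GPs who increased would be read as a rise in vaccination activity when part of it is longer observation.

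**Working it through.** **Step 1. Where each regression in Section 4.2.4 gets its arm term.**

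| Item | Source of the arm comparison |
|---|---|
| (1), (2) | Analogous to the primary model; the arm coefficient is assessed explicitly |
| (3) | None listed |
| (4) | Study arm named among the covariates |
| (5) | Analogous to item (4), so taken over |

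Item (3) is the only regression with no route to an arm coefficient.

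**Step 2. Windows.** Pb is three months (Section 2.8). T6 is six months after T0 (Section 2.8), and outcomes count uptake from T0 to the time point (Section 7). The ratio of window lengths is 6/3 = 2.

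**Step 3. Effect on the score.** The SAP gives no figure for this objective and no baseline dose rates, so there is nothing to reproduce and the rates below are assumptions. Let a GP have a constant rate of λ doses per three months. Take the baseline count as Poisson(λ) and the follow-up count as an independent Poisson with mean 2λ (T0 to T6) or λ (a matched three-month window). Put both into the SAP's four categories, with probabilities a0 to a3 at baseline and b0 to b3 at follow-up. Score an increase when the follow-up category is higher:

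P(increase) = a0(b1 + b2 + b3) + a1(b2 + b3) + a2·b3

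Example, λ = 4: a = (0.0183, 0.7668, 0.2120, 0.0028). For the six-month mean of 8, b = (0.0003, 0.1909, 0.6246, 0.1841).

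- Six months: 0.0183×0.9997 + 0.7668×0.8087 + 0.2120×0.1841 = 0.0183 + 0.6201 + 0.0390 = 0.68.
- Matched (b = a): 0.0183×0.9817 + 0.7668×0.2148 + 0.2120×0.0028 = 0.0180 + 0.1647 + 0.0006 = 0.18.

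| λ per 3 months (assumed) | P(increase), six-month count | P(increase), matched window | P(top category at baseline) |
|---|---|---|---|
| 1 | 0.33 | 0.23 | 0.00 |
| 2 | 0.32 | 0.13 | 0.00 |
| 3 | 0.53 | 0.12 | 0.00 |
| 4 | 0.68 | 0.18 | 0.00 |
| 6 | 0.77 | 0.27 | 0.04 |
| 8 | 0.77 | 0.27 | 0.18 |
| 10 | 0.58 | 0.28 | 0.42 |
| 12 | 0.35 | 0.23 | 0.65 |
| 15 | 0.12 | 0.10 | 0.88 |

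The rate does not change in any row. The fall at high rates comes from the open top category: a GP who starts there cannot move up in either window.

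**Step 4. Effect on the arm contrast.** Same model, with the control rate unchanged and the active rate multiplied by an assumed 1.5 at follow-up. Entries are P(increase), control to active, with the difference in brackets.

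| λ | Six-month count | Matched window |
|---|---|---|
| 2 | 0.315 to 0.606 (0.29) | 0.131 to 0.200 (0.07) |
| 3 | 0.533 to 0.840 (0.31) | 0.120 to 0.307 (0.19) |
| 4 | 0.678 to 0.908 (0.23) | 0.183 to 0.452 (0.27) |
| 8 | 0.767 to 0.815 (0.05) | 0.270 to 0.595 (0.33) |

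The longer window separates the arms better at 2 and 3 doses and worse at 4 and 8.

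**The case against.** **The arm omission is a drafting slip.** A list of what a model will include need not be exhaustive, and Section 4.1.2 makes the comparison between arms explicit. This is probably right about the intent. It does not repair the text: item (4) names the arm and item (3) does not. The closing paragraph of Section 4.2.4 allows models to be adapted after diagnostics, but diagnostics reveal neither a missing arm term nor unequal windows.

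**The mismatch is the same in both arms.** This stands. A reader might infer that the longer window biases the comparison or always dilutes it. The documents support neither inference. Both arms are observed for the same time, so no spurious difference arises from this alone, and Step 4 shows that the contrast can go either way.

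**An unchanged GP is not usually scored as increased.** This stands in part. The probability exceeds one half only from about 3 to 10 doses per three months. Section 2.1.1 admits GPs who gave no HPV doses in the previous six months, so low rates are plausible.

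**The T6 count could mean T3 to T6.** That would remove the mismatch, but Section 7 counts from T0.

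**Objective 2 already compares counts between arms.** It does, with baseline category as a candidate covariate kept only if its univariate p-value is at most 0.2. It compares levels, not change from Pb, so it does not answer objective 3.

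**The objective is exploratory.** Section 3.1 says so of all secondary outcomes. This limits the importance of the point but does not remove it.

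**Conclusion.** The point holds. As written, item (3) yields no estimate of the between-arm contrast that objective 3 asks for, leaves T3 and T12 without an analysis, and uses a definition of increase that does not mean a rise in rate. These conclusions rest on the text alone.

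The size of the scoring problem rests on assumptions: independent Poisson counts, chosen rates, accurate baseline categories, and increase read as a higher category. Over 1 to 8 doses per three months, an unchanged GP is scored as increased with probability 0.32 to 0.77, against 0.12 to 0.27 in a matched window.

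It would go too far to say that objective 3 cannot be measured with these data. Adding the arm term restores the comparison, and equal windows restore the meaning of the outcome. The primary objective is not affected. This should be fixed before the final analysis, but it is not a condition for the trial's main conclusion.

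**What to change.** Reword item (3) of Section 4.2.4:

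1. Add study arm and baseline HPV vaccination category to the covariates, and name the arm coefficient with its 95% confidence interval as the result.
2. Define increase as a higher category, on the four levels of Section 3.3.1, in a window as long as Pb. Use T0 to T3 as the main comparison and T3 to T6 (the T6 count minus the T3 count) for T6.
3. For T12, use a three-month-equivalent rate with a stated rounding rule, or drop T12 from the objective. A scaled count varies less than a true three-month count, so the match is only approximate.
4. Keep all randomised GPs in the main analysis, as the ITT rule in Sections 3.2 and 4.2.5 requires. State that GPs in the top baseline category cannot increase, and add a sensitivity analysis without them.
5. Since that category has no events by construction, its coefficient has no finite maximum-likelihood estimate. Name the remedy in advance, for example Firth's penalised likelihood.

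The cost is wording. Counts at T3 and T6 are already needed for objectives 1 and 2, so no additional data collection is required. The downside is that fewer GPs will be scored as increased, and at low dose rates the matched window may separate the arms less (Step 4).
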